4.2 Site Registration

This study is supported by the NCI CTSU.

IRB Approval

Sites participating with the NCI Central Institutional Review Board (NCI CIRB) must submit the Study Specific Worksheet for Local Context (SSW) to the CIRB using IRBManager to indicate their intent to open the study locally. The NCI CIRB's approval of the SSW is automatically communicated to the CTSU Regulatory Office, but sites are required to contact the CTSU Regulatory Office at [REDACTED] to establish site preferences for applying NCI CIRB approvals across their Signatory Network. Site preferences can be set at the network or protocol level. Questions about establishing site preferences can be addressed to the CTSU Regulatory Office by emailing the email address above or calling [REDACTED]

In addition, the Site-Protocol PI (*i.e.*, the investigator on the IRB/REB approval) must meet the following five criteria to complete processing of the IRB/REB approval record:

- Holds an Active CTEP status,
- Rostered at the site on the IRB/REB approval (*applies to US and Canadian sites only*) and on at least one participating roster,
- If using NCI CIRB, rostered on the NCI CIRB Signatory record,
- Includes the IRB number of the IRB providing approval in the Form FDA 1572 in the RCR profile, and
- Holds the appropriate CTEP registration type for the protocol.

Additional Requirements

Additional requirements to obtain an approved site registration status include:

- An active Federalwide Assurance (FWA) number,
- An active roster affiliation with the Lead Protocol Organization (LPO) or a Participating Organization, and
- Compliance with all protocol-specific requirements (PSRs).

4.2.1 Downloading Regulatory Documents

Download the site registration forms from the protocol-specific page located on the CTSU members' website. Permission to view and download this protocol and its supporting documents is restricted based on person and site roster assignment. To participate, the institution and its associated investigators and staff must be associated with the LPO or a PO on the protocol. One

way to search for a protocol is listed below.

- Log on to the [REDACTED] using your CTEP-IAM username and password,
- Click on *Protocols* in the upper left of your screen
 - Enter the protocol number in the search field at the top of the protocol tree, or
 - Click on the By Lead Organization folder to expand, then select LAO-11030, and protocol number 10246,
- Click on *Documents*, select *Site Registration*, and download and complete the forms provided. (Note: For sites under the CIRB initiative, IRB data will load automatically to the CTSU as described above.)

4.2.2 Requirements For NCI protocol #10246 Site Registration

- Site Initiation Visit
- Specimen Tracking System Training Requirement:
 - All data entry users (Clinical Research Associate role) at each participating site will need to complete the Theradex-led training.
 - Theradex will provide a certificate of completion, which will need to be submitted to the CTSU through the Regulatory Submission Portal.
 - The training is a one-time only requirement per individual. If an individual has previously completed the training for another ETCTN study, the training does not need to be completed again nor does the certificate of completion need to be resubmitted to the CTSU. However, new versions of the Specimen Tracking System may require new training.
 - This training will need to be completed before the first patient enrollment at a given site.
 - [REDACTED]

4.2.3 Submitting Regulatory Documents

Submit required forms and documents to the CTSU Regulatory Office via the Regulatory Submission Portal on the CTSU website.

To access the Regulatory Submission Portal, log on to the CTSU members' website, go to the Regulatory section, and select Regulatory Submission.

4.2.4 Checking Site Registration Status

Site's registration status may be verified on the CTSU website.

- Click on *Regulatory* at the top of the screen,
- Click on *Site Registration*, and
- Enter the site's 5-character CTEP Institution Code and click on Go.
 - Additional filters are available to sort by Protocol, Registration Status, Protocol Status, and/or IRB Type.

Note: The status shown only reflects institutional compliance with site registration requirements as outlined within the protocol. It does not reflect compliance with protocol requirements for individuals participating on the protocol or the enrolling investigator's status with NCI or their affiliated networks.

4.3 Patient Registration

4.3.1 OPEN / IWRS

The Oncology Patient Enrollment Network (OPEN) is a web-based registration system available on a 24/7 basis. OPEN is integrated with CTSU regulatory and roster data and with the Lead Protocol Organization (LPOs) registration/randomization systems or Theradex Interactive Web Response System (IWRS) for retrieval of patient registration/randomization assignment. OPEN will populate the patient enrollment data in NCI's clinical data management system, Medidata Rave.

Requirements for OPEN access:

- A valid CTEP-IAM account.
- To perform enrollments or request slot reservations: Be on an LPO roster, ETCTN Corresponding roster, or Participating Organization roster with the role of Registrar. Registrars must hold a minimum of an AP registration type.
- Have an approved site registration for a protocol prior to patient enrollment.

To assign an Investigator (IVR) or Non-Physician Investigator (NPiVR) as the treating, crediting, consenting, drug shipment (IVR only), or receiving investigator for a patient transfer in OPEN, the IVR or NPiVR must list the IRB number used on the site's IRB approval on their Form FDA 1572 in RCR. If a DTL is required for the study, the IVR or NPiVR must be assigned the appropriate OPEN-related tasks on the DTL.

Prior to accessing OPEN, site staff should verify the following:

- Patient has met all eligibility criteria within the protocol stated timeframes, and
- All patients have signed an appropriate consent form and HIPAA authorization form (if applicable).

Note: The OPEN system will provide the site with a printable confirmation of registration and treatment information. Please print this confirmation for your records.

████████████████████ from the OPEN link on the CTSU members' website.

[REDACTED]

Patient enrollment for this study will be facilitated using the Slot Reservation System in conjunction with the registration system in OPEN. Prior to discussing protocol entry with the patient, all site staff must use the CTSU OPEN Slot Reservation System to ensure that a slot on the protocol is available to the patient. Once a slot reservation confirmation is obtained, site staff may then proceed to enroll the patient to this study.

4.3.2 Special Instructions for Patient Enrollment

This Study will use the ETCTN Specimen Tracking System (STS).

- All biospecimens collected for this trial must be submitted using the ETCTN Specimen Tracking System (STS) unless otherwise noted.
- The system is accessed through Rave user roles: “Rave CRA” and “Rave CRA (Labadmin)” for data entry at the treating institutions and “Biorepository” for users receiving the specimens for processing and storage at reference labs and the Biorepository.
- Please refer to the Medidata Account Activation and Study Invitation Acceptance link on the CTSU website in the Data Management section under the Rave Home tab and then under Rave Resource Materials.
- **Important: Failure to complete required fields in STS may result in a delay in sample processing.** Any case reimbursements associated with sample submissions will not be credited if samples requiring STS submission are not logged into STS.

Detailed instructions can be found in Section 5.2.

4.3.3 OPEN/IWRS Questions?

[REDACTED]

[REDACTED]

4.4 **General Guidelines**

Participating sites are required to participate in a protocol-specific Site Initiation Teleconference prior to first patient registration.

Following registration, patients should begin protocol treatment within 7 to 14 business days. Issues

NCI Protocol #: 10246
Version Date: 02/16/2022

that would cause treatment delays should be discussed with the principal investigator. If a patient does not receive protocol therapy following registration, the patient's registration on the study may be canceled. The PI and study coordinator should be notified of treatment delays and/or cancelations as soon as possible.

5. BIOMARKER, CORRELATIVE, AND SPECIAL STUDIES

5.1 [REDACTED]

[REDACTED]	[REDACTED]	[REDACTED]	[REDACTED]	[REDACTED]	[REDACTED]	[REDACTED]	[REDACTED]	[REDACTED]
[REDACTED]	[REDACTED]	[REDACTED]	[REDACTED]	[REDACTED]	[REDACTED]	[REDACTED]	[REDACTED]	[REDACTED]
[REDACTED]	[REDACTED]	[REDACTED]	[REDACTED]	[REDACTED]	[REDACTED]	[REDACTED]	[REDACTED]	[REDACTED]
[REDACTED]	[REDACTED]	[REDACTED]	[REDACTED]	[REDACTED]	[REDACTED]	[REDACTED]	[REDACTED]	[REDACTED]
[REDACTED]	[REDACTED]	[REDACTED]	[REDACTED]	[REDACTED]	[REDACTED]	[REDACTED]	[REDACTED]	[REDACTED]
[REDACTED]	[REDACTED]	[REDACTED]	[REDACTED]	[REDACTED]	[REDACTED]	[REDACTED]	[REDACTED]	[REDACTED] L
[REDACTED]	[REDACTED]	[REDACTED]	[REDACTED]	[REDACTED]	[REDACTED] ent	[REDACTED]	[REDACTED]	[REDACTED]

Priority	Biomarker Name	Biomarker Assay	Biomarker Type and Purpose	M/O	Timing	Specimen	Quantity Needed	Laboratory
6	[REDACTED]	[REDACTED]	[REDACTED]	[REDACTED]	[REDACTED]	[REDACTED]	[REDACTED]	[REDACTED]
7	Belinostat PK profile	PK profile	Integrated PK profiling	M	Cycle 1 Day 1-2: Belinostat sampling schedule ^a	Blood	5 mL	APC, [name], Johns Hopkins University
8	MLN4924 (pevonedistat) PK profile	PK profile	Integrated PK profiling	M	Cycle 1 Day 1-2: MLN4924 (pevonedistat) sampling schedule ^b	Blood	5 mL	QPS, LLC

^a See belinostat sampling schedule, Section 5.3.3.2.1.

^b See MLN4924 (pevonedistat) sampling Section 5.3.3.1.1.

^c Blood collection is mandatory provided that there are anticipated to be at least 10% blasts in the baseline sample (a determination made based on review of routine clinical CBC and differential). When blood is not anticipated to meet the 10% blast sampling threshold, and if an optional bone marrow is being done, collection of aspirate is allowed in lieu of blood sampling if the aspirate sample is anticipated to meet the 10% blast sampling threshold.

^d Blood collection is mandatory provided that there are anticipated to be at least 40% blasts in the baseline sample (a determination made based on review of routine clinical CBC and differential). When blood is not anticipated to meet the 40% blast sampling threshold, and if an optional bone marrow is being done, collection of aspirate is allowed in lieu of blood sampling if the aspirate sample is anticipated to meet the 40% blast sampling threshold.

M=Mandatory, O=Optional, IHC=Immunohistochemistry, NCI=National Cancer Institute, PADIS= Pharmacodynamic Assay Development & Implementation Section, RT-PCR=reverse transcription polymerase chain reaction, VCU= Virginia Commonwealth University, CTRL=Clinical and Translational Research Laboratory, NGS=Next Generation Sequencing, PK=Pharmacokinetics, APC=Analytical Pharmacology Core laboratory

5.2 Specimen Tracking System Instructions

5.2.1 Specimen Tracking System Overview and Enrollment Instructions

For the ETCTN STS, the following information will be requested:

- Protocol Number
- Investigator Identification
 - Institution and affiliate name
 - Investigator's name
- Eligibility Verification: Patients must meet all the eligibility requirements listed in Section 3
- Additional Requirements:
 - Patients must provide a signed and dated, written informed consent form.

Upon enrolling a patient, IWRS will communicate with OPEN, assigning two separate and unique identification numbers to the patient, a Universal patient ID (UPID) and a Treatment patient ID. The UPID is associated with the patient and used each and every time the patient engages with the portion of this protocol that uses the ETCTN Specimen Tracking System. The UPID contains no information or link to the treatment protocol. IWRS will maintain an association between the UPID for ETCTN biobanking and molecular characterization and any treatment protocols the patient participates in, thereby allowing analysis of the molecular characterization results with the clinical data.

Immediately following enrollment, the institutional anatomical pathology report for the diagnosis under which the patient is being enrolled must be uploaded into Rave. The report must include the surgical pathology ID (SPID), collection date, block number, and the IWRS-assigned UPID and patient study ID for this trial. For newly acquired biopsies, the radiology and operative report(s) must also be uploaded into Rave. **Important:** Remove any personally identifying information, including, but not limited to, the patient's name, initials, medical record number, and patient contact information from the institutional pathology report prior to submission.

For questions regarding the Specimen Tracking System, please contact the [REDACTED] at [REDACTED]

A shipping manifest **must** be included with all sample submissions

Submitted specimens may be labeled using the label-generation utility in STS or labels generated outside STS. Labels generated outside STS must contain information as outlined in applicable specimen handling sections.

5.2.2 Specimen Labeling

5.2.2.1 Blood and/or Bone Marrow Aspirate Specimen Labels

Please refer to handling section for each specimen type in Sections 5.3 and 5.4.

For Blood Labels generated through the STS:

- Patient Study ID
- Universal Patient ID (UPID)
- Specimen ID (automatically generated by Rave)
- Time point
- Specimen type (e.g., blood, serum)
- Collection date, time, and specimen code (See Section 5.2.2.2) (to be added by hand)

[figure not shown]
5.2.2.2 Specimen Code to Include on the Label:

Biomarker Name	Specimen code
[REDACTED]	[REDACTED]
Belinostat PK profile	PK-Belinostat
MLN4924 (pevonedistat) PK profile	PK-PEVO

IHC=Immunohistochemistry, RT-PCR=reverse transcription polymerase chain reaction, PD=pharmacodynamics, PG=pharmacogenetic, PK=pharmacokinetics, WB=western blot, FC=flow cytometry.

5.2.2.3 Example of Specimen Label (Generated through RAVE STS)

The following image is an example of a tissue specimen label printed on a standard Avery label that is 1” high and 2.625” wide.

The QR code in the above example is for the Specimen ID shown on the second line.
NOTE: The QR code label is currently under development at Theradex as of 31-Aug-2018; therefore, labels generated by the STS for this study may not include a QR code.

The second line item from the end includes four data points joined together:

1. Tissue only: Primary (P), Metastatic (M), Normal (N) tissue indicated at the beginning of the specimen ID; this field is blank if not relevant (*e.g.*, for blood)
2. Block ID or blank if not relevant
3. SPID (Surgical Pathology ID) or blank if none
4. The last alpha-numeric code is protocol specific and is only included if the protocol requires an additional special code classification

The last line on the example label is for the handwritten date and optional time.

5.2.3 Overview of Process at Treating Site

5.2.3.1 OPEN Registration

All registrations will be performed using the Oncology Patient Enrollment Network (OPEN) system. OPEN communicates automatically with the Interactive Web Response System (IWRS) which handles identifier assignments, any study randomization and any prescribed slot assignments. If specimen analysis is required to determine eligibility, the protocol will be setup with multi-step registration.

Registration without eligibility specimen analysis:

1. Site enters registration data into OPEN during one or more steps.
2. IWRS receives data from OPEN, generates the Patient Study ID and the Universal Patient ID, both of which are sent back to OPEN.
3. IWRS sends all applicable registration data directly to Rave at the end of the final registration step.

Registration with eligibility specimen analysis - *not applicable for this trial.*

Any data entry errors made during enrollment should be corrected in Rave.

5.2.4 Specimen Tracking System Overview and Enrollment Instructions

5.2.4.1 Rave Specimen Tracking Process Steps

Step 1: Complete the Histology and Disease form (but do not upload reports until a specimen label can be applied to them) and the Baseline forms regarding Prior Therapies. Enter the initial clinical specimen data:

- Specimen Tracking Enrollment CRF: Enter Time Point, Specimen Category, Specimen Type, Block number, Tissue type, Surgical Path ID, and number of labels needed (include extra labels to apply to reports to be uploaded). CRF generates unique Specimen ID.

Step 2: Print labels using report in EDC and collect specimen.

- Label specimen containers and write collection date [if the study also requires recording the collection time on the label, include the time] on each label.
- After collection, store labeled specimens as described in Sections 5.3 and 5.4.
- Apply an extra specimen label to each report before scanning. Return to the Histology and Disease form to upload any initial Pathology, Radiology, Molecular Reports (up to 4), Surgical (or Operative) reports and Pathology Verification form (when applicable). Return to Specimen Tracking Enrollment CRF to upload any molecular report (one per specimen) and/or specimen specific pathology or related report (one per specimen). Uploaded reports should have protected health information (PHI) data, like name, mailing address, medical record number or social security number (SSN), redacted. Do not redact SPID, block number or relevant dates, and include the UPID and patient study ID on each document.

█ [REDACTED]

[REDACTED]

[REDACTED]

5.3.1.1 Collection of Specimen(s)

Paired samples of bone marrow aspirate (optional, from consenting patients) or blood will be collected when the baseline sample is anticipated to contain $\geq 10\%$ blasts.

Collect paired (pre- and 24 hr post-treatment) samples of either blood (10 mL) or, from consenting patients, bone marrow aspirate (5 mL) in 10mL Streck tubes provided by the PADIS laboratory (see supply ordering information below). The same sample type (blood or bone marrow aspirate) must be used for both samples.

5.3.1.2 PADIS/Streck tube supply ordering

Prior to collection, e-mail a request for specimen collection and shipping materials to [REDACTED]. Allow at least 6 business days for receipt of materials. A confirmation email with expected shipping date will be sent. Refer to the reference document "NCI-PADIS SOP for Streck Tube Samples" available on the CTSU website in the Supplemental Documents section for NCI-10246.

5.3.1.3 Handling of Specimen(s)

Samples may be held at room temperature until shipment on the day of collection. Samples being submitted to NCI-PADIS will be labeled as follows or labeled using the RAVE Specimen Tracking System.

Labels generated outside STS should mimic the STS labeling format as shown below:

- Patient ID: Protocol # (10246) - Treatment ID # (assigned at enrollment) – UPID (assigned in STS)
- Specimen ID: Protocol # (10246) - UPID plus sequentially generated integer (assigned in STS)
- Code: PD-IHC
- Type: Blood or Bone marrow
- Time Point: pre-dose or post-dose
- Date/time collected

5.3.1.4 Shipping of Specimen(s)

Specimens must be shipped at room temperature to the PADIS laboratory on the day of collection. The collected specimens are stable for up to 48 hours at room temperature (15°C to 30°C) prior to processing (per PADIS laboratory standards). Do not collect samples late in the day on Thursdays past the time in which it is possible to ship samples to PADIS for receipt on Friday morning and do not collect on Fridays, as PADIS is closed on Saturdays and Sundays. Also, do not collect and ship samples on the day before a federal holiday.

A sample inventory must accompany all shipments.

[REDACTED]

[REDACTED]

[REDACTED]

[REDACTED]

5.3.1.5 Site(s) Performing Correlative Studies

The NCI Pharmacodynamic Assay Development and Implementation Section (PADIS) laboratory will conduct this study.

5.3.2 RT-PCR of Pharmacodynamic Markers

RT-PCR will be performed to assess pharmacodynamic markers for drug response. The assay includes 2 integrated target genes: NQO1 and SLC7A11. Sampling for PD-RTPCR analysis is mandatory.

5.3.2.1 Collection of Specimen(s)

- Blood samples will be collected pre-treatment and 6 hr post-treatment. Collect 2.5 mL of blood in PAXgene RNA tube (see supply ordering information below).
- Ensure that the PAXgene tube is at room temperature (18°C–25°C) prior to use and properly labeled with patient identification.
- Using a blood collection set, collect blood into the PAXgene Blood RNA Tube using your institution's recommended standard procedure for venipuncture.
- Hold the PAXgene blood RNA tube vertically, below the donor's arm during blood collection.
- Allow at least 10 seconds for a complete blood draw to take place. Ensure that the blood has stopped flowing into the tube before removing the tube from the holder.

5.3.2.1.1 Asuragen/PAXgene tube supply ordering

Each participating site will procure PAXgene tubes. Recommended items/vendors include:

- BD Biosciences Catalog No. 762165: PAXgene® Blood RNA Tube 2.5mL
- Fisher Scientific Catalog No. 23-021-01 (Manufacturer No. 762165): BD PAXgene™ Blood RNA Tube 2.5mL
- QIAGEN Catalog No./ID 762125: PAXgene® Blood RNA Tube (IVD) 2.5mL

5.3.2.2 Handling of Specimen(s)

- Gently invert the PAXgene Blood RNA Tube 8 to 10 times.
- "Slow-freeze" the tube overnight at -20°C. The tube may then be transferred to a -70°C freezer for long-term storage.

[figure not shown]
Samples being submitted to Asuragen will be labeled as follows or labeled using the RAVE Specimen Tracking System.

Labels generated outside STS should mimic the STS labeling format as shown below:

- Patient ID: Protocol # (10246) - Treatment ID # (assigned at enrollment) – UPID (assigned in STS)
- Specimen ID: Protocol # (10246) – UPID plus sequentially generated integer (assigned in STS)
- Code: PD-RTPCR
- Type: Blood

- Time Point: pre or post
- Date/time collected

5.3.2.3 Shipping of Specimen(s)

5.3.2.4 Site(s) Performing Correlative Studies

This study will be conducted by Asuragen. Asuragen is a biotechnology company based in Austin, Texas involved in diagnostics and therapeutics. Asuragen's offerings include molecular diagnostic products providing identification of genetic abnormalities associated with oncology and genetic diseases.

5.3.3 Pharmacokinetic (PK) Studies

PK studies will be done to document PK findings and interactions, if any, between the study drugs. Sampling for PK analyses of both agents is mandatory.

Any circumstance which prevents collection, submission, or analysis of blood samples for PK studies should be reviewed with the principal investigator. PK samples will be collected, processed, and stored at the participating centers prior to shipment.

5.3.3.1 MLN4924 (pevonedistat) PK Studies

MLN4924 (pevonedistat) PK samples will be processed and shipped to QPS, LLC, for analysis.

5.3.3.1.1 Collection of Specimens MLN4924 (pevonedistat) Specimen(s)

- Whenever possible, collect PK specimens from a venous access point that has not been used for drug infusion, preferably using an 18G needle to avoid hemolysis.

- Collect 3 mL of venous blood into a **chilled** tube containing K2-EDTA (see tube ordering information below) at the time points specified below for MLN4924 (pevonedistat) PK analysis.
- GENTLY invert the tube 8-10 times to mix the additive with the collected blood prior to centrifugation and **place immediately on ice**.
- For MLN4924 (pevonedistat), sample collection will occur at these approximate time points on Cycle 1, starting on Day 1, timed from the **START** of the MLN4924 infusion:
 - pre-MLN4924 (pevonedistat) infusion
 - 30 minutes (± 10 min) after the **START** of the MLN4924 (pevonedistat) infusion, and then
 - 1 hr (± 10 min)
 - 2 hrs (± 10 min)
 - 2.5 hrs (± 10 min)
 - 5 hrs (± 30 min)
 - 8 hrs (± 45 min)
 - and 24hrs (± 4 hrs) after the **START** of MLN4924 (pevonedistat) infusion.

Note: if samples cannot be obtained within the stated time point window, it's preferable to draw a sample as close to the time point as possible rather than omitting the sample – be sure the actual time of collection is recorded

5.3.3.1.1.1 MLN4924 PK supply ordering

Each participating site will procure K2-EDTA tubes. Recommended items/vendors include: BD (Becton Dickinson) Catalog No. 02-689-03 (Manufacturer No. BD367835): K2EDTA-containing plastic lavender-top tubes 3 mL

- Fisher Scientific Catalog No. 367835: K2EDTA-containing plastic lavender-top tubes 3 mL

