5.3.3.2 Belinostat PK Studies

[REDACTED]

[REDACTED]

- Whenever possible collect PK specimens from a venous access point that has not been used for drug infusion.
- Collect 4-6 mL of venous blood into tubes containing sodium heparin (see tube ordering information below) at the time points specified below for belinostat PK analysis.
- GENTLY invert the tube 8-10 times after collection to avoid sample hemolysis.
- For belinostat, sample collection will occur at these approximate time points on Cycle 1, starting on Day 1, timed from the END of the belinostat infusion:
 - pre-belinostat infusion
 - 5 minutes (± 1 min) prior to the END of belinostat infusion
 - 15 minutes (± 10 min) after the END of the belinostat infusion and then
 - 30 minutes (± 10 min)
 - 1 hr (± 10 min)
 - 2 hrs (± 10 min)
 - 4 hrs (± 10 min)
 - 6 hrs (± 30 min)
 - 8 hrs (± 45 min)
 - and 24 hrs (± 4 hrs) after the END of the belinostat infusion.

Note: if samples cannot be obtained within the stated time point window, it's preferable to draw a sample as close to the time point as possible rather than omitting the sample – be sure the actual time of collection is recorded.

5.3.3.2.1.1 Belinostat PK supply ordering

Each participating site will procure sodium heparin tubes. Recommended items/vendors include:

- BD (Becton Dickinson) Catalog No. 23-021-017 (Manufacturer No. BD 367878): sodium heparin-containing plastic green-top tubes 6 mL
- Fisher Scientific Catalog No. 367878: sodium heparin-containing plastic green-top tubes 6 mL

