6.1.1 MLN4924 (pevonedistat)

MLN4924 (pevonedistat) will be given intravenously over 60 minutes (± 10 minutes) through central or peripheral venous access. The IV infusion can be slowed or stopped and restarted for any associated infusion-related reactions. The total time from the IV preparation to end of IV infusion must not exceed 6 hours if stored at room temperature. Alternatively, the prepared IV bag may be stored for up to 18 hours at 2°C to 8°C (36-46°F). After 18 hours of storage at 2°C to 8°C (36-46°F), the prepared IV bag must be used within 3 hours upon coming to room temperature or must be discarded. When both drugs are given on the same day (Days 1, 3, 5), start the MLN4924 (pevonedistat) infusion within 60 min after the completion of belinostat infusion.

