 - Do not shake; gently mix the IV solution by inverting the IV bag several times
 - Inspect the IV solution to ensure it is clear and free of visible particles
- Alternatively, a 250 mL **empty IV bag can be used:**
 - Add the required volume of D5W or NS into the empty IV bag
 - Add the calculated dose (mL) of pevonedistat o Final volume (250 mL) = Drug + D5W or NS
 - Do not shake; gently mix the IV solution by inverting the IV bag several times
 - Inspect the IV solution to ensure it is clear and free of visible particles

Materials: PVC or Polyolefin bags; non-DEHP IV bag is preferred but not required

Storage: Store MLN4924 (Pevonedistat HCl) refrigerated at 2°-8°C (36°-46°F) in its original

carton to protect from light.

If a storage temperature excursion is identified, promptly return MLN4924 (Pevonedistat HCl) to 2°-8°C (36°-46°F) and quarantine the supplies. Provide a detailed report of the excursion (including documentation of temperature monitoring and duration of the excursion) to [REDACTED] determination of suitability.

Stability: Stability studies are ongoing.

- Once MLN4924 (Pevonedistat) prepared IV solution is complete, the prepared IV solution must be used within 6 hours when stored at ambient room temperature. Discard the IV bag if it cannot be used within 6 hours.
- Alternatively, the prepared IV solution is stable up to 18 hours when stored at 2°-8°C (36°-46°F), after which the IV bag can be used within 3 hours upon removal from 2°-8°C storage. The prepared IV solution must be brought up to ambient room temperature before administering to patient. If cannot used within 3 hours, the prepared IV solution must be discarded.

Route of Administration: Intravenous

Method of Administration: Infuse over 60 minutes (+/- 10 minutes) through peripheral IV-line, midline or central venous access. The IV infusion can be slowed or stopped and restarted for any associated infusion-related reactions. The total time from the IV preparation to end of IV infusion must not exceed 6 hours. Infusion line can be flushed with 5% Dextrose in Water or 0.9% Normal Saline immediately after IV administration is complete. Protecting IV bag from light during IV infusion is not required.

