9.4.2 Statistical Analyses for Secondary Objectives

Toxicities: AEs and SAEs, dosing levels, treatment received, best clinical response, and demographics will be listed. Basic descriptive statistics will be used to summarize toxicities related to the study drugs by grade, and all toxicities, whether related or unrelated to the study drugs.

Anti-tumor activity: For the response rate calculations, all study reports will contain at least a section with all enrolled patients. Other sections of the reports may detail the response rate for response-evaluable patients only. All response rate analyses based on a subset of patients will be accompanied by explanations of which patients were excluded and the reasons; 95% confidence limits will be given. For patients who do not have disease progression or have not died at time of analysis, the last date the patient was known to be alive and progression free will be used for duration of response analysis. If there are at least 3 responses, duration of response and time to response will be summarized by the first, second, and third quantiles and illustrated by a Kaplan-Meier plot.

PK interactions: PK parameters in MLN4924 (pevonedistat) and in belinostat will be calculated using standard non-compartmental methods and summarized as geometric mean and geometric coefficient of variation. C_{max} and the times needed to reach these concentrations (t_{max}) will be assessed by inspection of the concentration versus time plots. The AUC will be calculated from time zero to infinity ($AUC_{0-\infty}$). V_d and $t_{1/2}$ will also be calculated accordingly. To discover any potential PK interactions between the 2 agents, each PK parameter will be compared with each referenced PK parameter for those who receive single-agent at the same amount dose by a one-sample t-test. The normality of the PK parameters will be checked, and data transformation may be performed if data are highly skewed.

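### No pevonedistat PK draw is tied to the end of the infusion, so observed Cmax and tmax carry avoidable timing noise (minor; secondary PK objective)

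*Combined protocol and SAP*

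**What the plan says.** **Pevonedistat sampling (5.3.3.1.1).** "For MLN4924 (pevonedistat), sample collection will occur at these approximate time points on Cycle 1, starting on Day 1, timed from the" START of the infusion. After the pre-infusion sample, draws follow at 30 min, 1 h, 2 h and 2.5 h (each ±10 min), 5 h (±30 min), 8 h (±45 min) and 24 h (±4 h). No draw is defined by the end of infusion. Out-of-window draws are preferred to omitted ones, and sites are told: "be sure the actual time of collection is recorded".

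**Pevonedistat infusion.** Section 8.1.1 says "Infuse over 60 minutes (+/- 10 minutes) through peripheral IV-line, midline or central venous access". Section 6.1.1 adds "The IV infusion can be slowed or stopped and restarted for any associated infusion-related reactions". Neither section says how PK draws are re-timed when that happens.

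**Belinostat sampling (5.3.3.2).** One draw is set at 5 min (±1 min) "prior to the END of belinostat infusion", and the later draws are timed from END.

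**Analysis (9.4.2).** Cmax and tmax "will be assessed by inspection of the concentration versus time plots". To look for an interaction, "each PK parameter will be compared with each referenced PK parameter for those who receive single-agent at the same amount dose", by a one-sample t-test. Section 9.4 describes all analyses as descriptive.

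**The concern.** Under a constant-rate infusion the plasma concentration peaks when the infusion stops. A draw before that point catches the rising limb and a draw after it catches the decline, so a mistimed draw reads low in both directions and the errors do not average out across patients. In this plan the draw and the end of infusion each move within their own 20-minute window, and nothing links them.

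The parameters at stake are pevonedistat Cmax and tmax. They serve objective 1.2.4 (PK interactions). They also bear on two aims in Section 2.5: whether plasma levels reach those active in vitro, and how exposure relates to pharmacodynamics and response. PK is among the data reviewed before the 59 mg/m² level opens. Escalation cohorts hold three to six evaluable patients, so one or two badly timed peaks can move a cohort summary.

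Recording the actual draw time lets AUC be computed on true times. It cannot recover a peak that was not sampled.

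**Working it through.** The plan states no figure to reproduce. The check has two parts.

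**1. Offset between draw and end of infusion (protocol windows only).** Both are measured from START, and offset = draw time − end time. The end of infusion falls at 50 to 70 min.

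- 30 min draw (20 to 40 min): 20 − 70 = −50 to 40 − 50 = −10 min.
- 1 h draw (50 to 70 min): 50 − 70 = −20 to 70 − 50 = +20 min.
- 2 h draw (110 to 130 min): 110 − 70 = +40 to 130 − 50 = +80 min.

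Only the 1 h draw can land on the peak. If draw and end times are independent and uniform over their 20-min windows (an assumption):

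- mean absolute offset = 20/3 = 6.7 min;
- P(offset over 10 min) = (1 − 10/20)² = 25%;
- P(offset over 15 min) = (1 − 15/20)² = 6%.

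If the infusion runs 90 to 100 min, the 1 h draw falls 20 to 50 min before the end (90 − 70; 100 − 50), and the 2 h draw 10 to 40 min after it (110 − 100; 130 − 90).

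**2. Effect on observed Cmax (assumed model).** No pevonedistat half-life is given, so a one-compartment model with constant-rate infusion was run over assumed half-lives h of 30 to 480 min, with k = ln 2/h.

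- Draw d min after the end: observed/true = 2^(−d/h).
- Draw at time t during an infusion of length T: observed/true = (1 − e^(−kt))/(1 − e^(−kT)).

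At the extreme corners:

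- 20 min late: a loss of 37%, 21%, 11% and 3% at h = 30, 60, 120 and 480.
- 50 min into a 70-min infusion: the 1 h draw is 15%, 21%, 25% and 28% low. At h = 480 the 2 h draw limits the damage, because 50 min after the end it reads 2^(−50/480) = 0.93.

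Across the windows, with uniform times and Cmax taken as the highest observed sample, observed/true Cmax is as follows. The tied draw is 5 ±1 min before END, with the other draws unchanged.

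| Half-life (min) | Current: mean / SD / worst | Tied draw: mean / SD / worst | 90–100 min infusion, mean: current / tied |
|---|---|---|---|
| 30 | 0.91 / 0.08 / 0.63 | 0.96 / 0.01 / 0.93 | 0.84 / 0.99 |
| 60 | 0.93 / 0.05 / 0.79 | 0.94 / 0.01 / 0.91 | 0.78 / 0.97 |
| 120 | 0.94 / 0.05 / 0.75 | 0.93 / 0.01 / 0.89 | 0.87 / 0.96 |
| 240 | 0.95 / 0.05 / 0.82 | 0.92 / 0.01 / 0.89 | 0.93 / 0.95 |
| 480 | 0.97 / 0.03 / 0.90 | 0.92 / 0.01 / 0.89 | 0.97 / 0.97 |

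The tied draw narrows the offset range from 40 min (−20 to +20) to 2 min (−6 to −4), whatever the infusion length. At half-lives of 120 min and longer with an uninterrupted infusion, its mean is slightly lower than now, because it always samples about 5 min short of the peak.

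**The case against.** **The 1 h draw already targets the nominal end of a 60-min infusion.** This stands. A reader might infer that Cmax itself is typically measured 20 min away from the peak. The documents do not support that: 20 min is the corner of two windows, it describes the 1 h draw, and Cmax is read from the whole profile.

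**The size depends on a half-life that nobody can look up here.** This stands, and it is why a range is shown. Section 2.2.1.2 gives belinostat a half-life of 0.3 to 1.3 h, and its infusion is 30 min, so a tight end-of-infusion draw may matter more for that drug. Different schedules for two drugs are not in themselves a defect.

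**The effect on the interaction test is unknown.** A reader might infer that mistiming will create or hide an interaction. That depends on how the single-agent reference studies were sampled, which the documents do not say. If their draws were also timed from START, much of the average shortfall would cancel, and an END-tied draw could introduce a mismatch. This stands as the main downside of the change.

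**Stop times may be captured elsewhere.** The PK section asks only for the collection time, but the dosing case report forms are not in these documents. It cannot be said that stop times go unrecorded.

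**The objective is secondary and descriptive.** This also stands. The review before 59 mg/m² weighs toxicity, PK and clinical data together, with no stated Cmax criterion, and MTD/RP2D rests on DLT counts.

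None of this gives a reason to leave the peak draw unlinked to the event it is meant to capture.

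**Conclusion.** The point holds as a minor, inexpensive improvement. No pevonedistat draw is tied to the end of infusion. The 1 h draw can miss it by up to 20 min within the windows, about 7 min on average under uniform timing, and by more when the infusion is prolonged.

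Under the assumed one-compartment model with half-lives of 30 to 480 min, the average understatement of Cmax is about 3% to 9%, the timing SD is 0.03 to 0.08, and the worst case reads 0.63 to 0.90 of the true peak. For infusions of 90 to 100 min the mean is 0.78 to 0.97. The documents give no frequency for such infusions.

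The gain from a tied draw is precision and protection against long infusions. A reader might expect it to remove a large mean bias, but the model does not show that: the mean is 0.92 to 0.96 with the tied draw, against 0.91 to 0.97 now. AUC is little affected when actual times are used, and the dose-escalation and RP2D rules are untouched.

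**What to change.** In 5.3.3.1.1, replace the 1 h draw with one tied to the actual END of the pevonedistat infusion in a tight window, for example 5 ±1 min before END, as already done for belinostat. Ask for actual infusion start, stop and interruption times with the PK record, unless the dosing forms already capture them. The later draws may stay timed from START, since re-anchoring them adds little once actual times are known.

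In 9.4.2, state the sampling schedule of the single-agent reference whenever Cmax or tmax is compared, so that any mismatch is visible.

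The cost is an edited line in 5.3.3.1.1 and in any site sampling instructions, plus a sentence in 9.4.2. It needs no extra tube or visit and changes nothing in dosing or patient management. Staff do have to anticipate the end of infusion, as they already do for belinostat.
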